8.2 Response Rate

For measurable disease response, RECIST 1.1 criteria will be used. The Prostate Cancer Clinical Trials Working Group (PCWG2) criteria will be used to determine a PSA response [15]. PCWG2 recommends a two-objective paradigm in metastatic CRPC: (1) controlling, relieving, or eliminating disease manifestations that are present when treatment is initiated and (2) preventing or delaying disease manifestations expected to occur. PSA decline, changes in imaging will also be reported. The progression for measurable disease will be per RECIST1.1 criteria, and for bone metastases will be per PCWG2.

8.3 Duration of overall response

The duration of overall response is measured from the time measurement criteria are met for CR/PR (whichever is first recorded) until the first date that recurrent or progressive disease is objectively documented (taking as reference for progressive disease, the smallest measurements recorded since the treatment started).

8.4 Duration of stable disease

Stable disease is measured from the start of the treatment until the criteria for progression are met, taking as reference the smallest measurements recorded since the treatment started. Tumor evaluations are recommended every three cycles while on protocol therapy and then as clinically required by the treating physician.

8.5 Time to Treatment Failure:

From date of registration to date of progressive disease, or date patient is taken off study for any reason. All patients, regardless of the number of completed cycles of therapy, will be included for toxicity evaluation. All subjective toxicities encountered during the study will be evaluated according to the NCI toxicity criteria. Objective toxicities will be based upon the greatest severity that occurred at any time during a treatment cycle and not on the severity noted at the beginning of the next cycle.

8.6 Time to Progression:

From date of registration to date of progressive disease, defined as either progression of measurable disease by RECIST 1.1 criteria, or progression of bone metastases or occurrence of new skeletal related event or by PSA per PCWG 2 criteria [Appendix B].

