3.2 Bicalutamide (Casodex®) (NSC-722665)

For bicalutamide, goserelin acetate, and leuprolide acetate, commercially

Available preparations are used as per the FDA approved dose, route and schedule. Information about commercial drugs is publicly available in the Physician's Desk Reference (PDR), prescribing information and other resources.

Chemistry: Bicalutamide is a racemic mixture containing two enantiomers, (2RS)-4'-Cyano-3(4-fluorophenylsulphonyl)-2-hydroxy-2-methyl-3'-trifluoromethyl propionanilide. Bicalutamide is an active non-steroidal antiandrogen and its antiandrogen activity resides exclusively in the (-) or (R) enantiomer. Unlike flutamide, it is peripherally selective and does not cause a rise in serum LH or Testosterone in male rats and dogs. This peripheral selectivity may be because it penetrates poorly the CNS and Hypothalamus (the site of negative feedback of androgens). In humans, rises in LH, Testosterone and Estradiol concentrations were seen. These rises were not dose related. In 90%, testosterone levels remained within normal limits. There was no significant rise in mean serum FSH.

Bicalutamide has been given to over 3,500 men in 35 different clinical studies worldwide, in doses up to 600 mg daily.

Adverse Effects:

When bicalutamide is given in combination with an LHRH analog, the pharmacologic adverse event profile is dominated by the LHRH analog and includes hot flashes (53%), gynecomastia (9%) and breast pain (6%). Other adverse events reported regardless of causality included diarrhea (12%), constipation (22%), nausea (15%) and abdominal pain (11%). Other adverse events were reported, such as fatigue (22%), pain (35%), back pain (25%), pelvic pain (21%), infection (18%), peripheral edema (13%), dyspnea (13%), nocturia (12%), hematuria (12%), anemia (11%), dizziness (10%). Bicalutamide has been associated with changes in liver function, although these are infrequent (7%) and rarely occur with jaundice.

Many of these changes improved or resolved despite continuation of bicalutamide therapy. There have been no reports of fatal hepatotoxicity associated with bicalutamide therapy.

Pharmacology

Pharmacokinetics:

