4.0 ELIGIBILITY CRITERIA

4.1 Inclusion Criteria:

1. Histologically confirmed prostate adenocarcinoma with metastasis either starting or recently started on LHRH analogue therapy. [Late induction permitted within 3 months of starting LHRH analogue therapy or antiandrogen] All patients who have not initiated hormone therapy (Early induction patients) must have elevated PSA ≥ 4 ng/ml within 28 days prior to registration. For late induction registrations, PSA must be ≥ 4 ng/ml prior to start of androgen deprivation therapy; either antiandrogen or LHRH analogue or GNRH antagonist .If patients are on antiandrogen, this will need to be discontinued for at least 7 days prior to registration.
2. Patients with a history of prior neoadjuvant or adjuvant hormone therapy are eligible provided they have received twenty four or less months of hormone treatment (single or combination treatment, excluding orchiectomy). Neoadjuvant/adjuvant hormone therapy must have been discontinued at least 6 months prior to registration. This is intended to exclude patients who might have been rendered indirectly androgen insensitive.
3. There must be no plans to receive concomitant chemotherapy, biological response modifiers, radiation therapy or hormonal therapy. Concomitant radiation therapy is allowed for the palliation of severe pain/neuropathic compression.
4. Prior or concomitant use of megestrol acetate for the treatment of hot flashes is allowed.
5. Patients must have a performance status of 0 - 2 by Zubrod Criteria.
6. Patients must have recovered from any major infections and/or surgical procedures and, in the opinion of the investigator, not have significant active medical illness precluding protocol treatment or survival.
7. No prior malignancy is allowed except for adequately treated basal cell (or squamous cell) skin cancer, superficial or in situ cancer of the bladder. For an invasive cancer the patients should be disease free for at least 3 years prior to enrollment on study.
8. For all patients a bone scan must be performed within 60 days prior to registration for tumor assessment. CT scans (abdomen and pelvis) and chest x-ray are optional, but must be repeated if used for disease assessment. For late induction registrations, tumor assessment imaging showing metastatic disease must be available prior to start of androgen deprivation therapy.
9. Age 18 or older and willing and able to provide informed consent.

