10. Willingness to swallow pills and no medical condition that would interfere with this.
11. Male patient and his female partner who is of childbearing potential must use 2 acceptable methods of birth control (one of which must include a condom as a barrier method of contraception) starting at screening and continuing throughout the study period and for 3 months after final study drug administration. Patients are also required to use a condom if having sex with a pregnant woman.
12. Patient should agree to a tumor tissue biopsy prior to protocol enrollment. Post therapy biopsy is optional.
13. Patients who are being treated with a GNRH antagonist should be willing to switch to a LHRH analogue after registration.
14. Patients must have one of the following a) Low volume disease (defined as no visceral metastases and < 4 bone metastases) or b) are not candidates for docetaxel based chemotherapy or 3) refused docetaxel chemotherapy

4.2 Patients must NOT meet any of the following exclusion criteria:

1. History of seizure or any condition that may predispose to seizure (e.g., prior cortical stroke, significant brain trauma) at any time in the past. Also, history of loss of consciousness or transient ischemic attack within 12 months of Day 1 visit;
2. Known or suspected brain metastasis or active leptomeningeal disease;
3. Severe concurrent disease, infection, or co-morbidity that, in the judgment of the Investigator, would make the patient inappropriate for enrollment;
4. Absolute neutrophil count < 1,000/ μ L, or platelet count < 50,000/ μ L, or hemoglobin < 8 /dL) at the Screening visit.
5. Total bilirubin, alanine aminotransferase (ALT) or aspartate aminotransferase (AST) > 2.5 times the upper limit of normal
6. Creatinine > 177 μ mol/L (2 mg/dL)
7. Clinically significant cardiovascular disease including:
 - Myocardial infarction within 6 months;
 - Uncontrolled angina within 3 months;
 - Congestive heart failure New York Heart Association (NYHA) class 3 or 4, or patients with history of congestive heart failure NYHA class 3 or 4 in the past, unless screening echocardiogram or multi-gated acquisition scan performed within 3 months results in a left ventricular ejection fraction that is \geq 45%;

---History of clinically significant ventricular arrhythmias (e.g., ventricular tachycardia, ventricular fibrillation, torsades de pointes);

---History of Mobitz II second degree or third degree heart block without a permanent pacemaker in place;

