Karmanos Cancer Institute. Training and support will be provided for all staff entering data. Data entry must occur within 2 weeks of visits along with submission of applicable source documentation. The only concomitant medication data to be submitted is administration of bisphosphonate or denosumab.

5.2 Stratification and randomization procedures:

The registering data manager will first stratify the patient by race (AA or other) and cancer related bone pain at diagnosis of metastatic disease (present or absent) into one of 4 strata. Even if pain is well controlled/resolved at present the patient will be considered positive for bone pain. The patient will then be randomized to Arm A or Arm B using the stratum-appropriate randomization list prepared in advance by the study statistician [name]. Arms A and B are defined in the Study Schema (on page 5) and in Section 5.3 below. Each of the 4 randomization sequences will use random permuted blocks of varying sizes. The treatment arm randomization and enrollment confirmation will be communicated to site staff in writing within 24-48 hours from receipt of all eligibility source documents. Study treatment should start within 7 days of registration.

5.3 Study design and plan:

Overall Study Design and Plan

This study is a multicenter Phase II, randomized, screening study of oral MDV3100 (160 mg/day) in patients with metastatic hormone sensitive prostate cancer. Patients must not have received prior cytotoxic chemotherapy for metastatic disease. Radiation therapy, and initiation of

bisphosphonates or other approved bone targeting agents, and standard of care steroid and pain management are allowed and should not result in discontinuation of study drug therapy.

For patients eligible for late induction registration the treatment start date will be the date of initiation of GNRH analogue or antagonist, with or without antiandrogen. Late induction patient visits will be adjusted based on the length of their prior hormone therapy. Study drug therapy should be continued as long as the patient is tolerating the study drug and continues androgen deprivation therapy or until confirmed radiographic disease progression or a skeletal related event AND one of the two following events: 1) initiation of another agent for treatment of prostate cancer. Or 2) Intolerance to therapy.

Patients will be randomized to receive either:

ARM A

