5.4 Agent Administration

Starting doses of the agents are as follows:

Enzalutamide is provided as 40 mg soft gelatin capsules in bottles with induction-sealed childresistant caps.

Directions for Administration

Study drug doses should be taken as close as possible to the same time each day. All study patients on enzalutamide will take 4 capsules of study drug once daily unless dose adjustment has been done. Patients randomized to bicalutamide will take 1 tab of 50 mg daily dose. If dosing is missed on one day for any reason, double-dosing should NOT occur the following day. The oral medications can be taken with or without food. Documentation of daily dose will be conducted by patient on a study diary.

Storage and Labeling

Study drug should be stored in a secure location with limited access within the following temperature range: 59°F to 86°F (15°C to 30°C). Bottles will be labeled with the study protocol number, medication or bottle number, contents, directions for use, storage directions. Patients will be instructed to store study drug at room temperature out of the reach of children.

6.0 TOXICITIES TO BE MONITORED AND DOSAGE MODIFICATION:

All toxicities will be graded as per NCI Common Toxicity (CTCAE) version 4.0.

Toxicity evaluation will be done monthly for the first 8 visits starting with day 1 and after that every 3 months until progression. Radiologic evaluation at months 6 and 12 with scans (CT scans and bone scan), and PSA levels every month for the first 8 visits and after that every 3 months. After 12 months radiologic evaluation is required annually while patient is on study.

Dose Reduction/Dose Adjustment

Patients who experience a Grade 3 or greater toxicity that is attributed to study medication, and cannot be ameliorated by the use of adequate medical intervention should have their treatment interrupted until the toxicity improves to a Grade 2 or lower severity. Patients may subsequently be re-started on study drug, including at a reduced dose (80 mg daily of enzalutamide), with the written approval of the PI (or designee). **Any reports of seizure activity for patients randomized to enzalutamide require immediate and permanent discontinuation of this therapy.**

There are no dosage adjustments for hematologic toxicity.

Dosage adjustments for Non-hematologic Toxicity: a.

Diarrhea Toxicity:

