11.6 Analysis

11.6.1 For the primary objective, the binary endpoint (PSA remission at month 7, yes/no) will be summarized with its point estimate (an occurrence rate), and 2-sided Wilson type 95% confidence interval (CI). This analysis will be performed two ways: a) for all randomized patients (the intention to treat subset); and b) for all r-e patients (the per protocol subset). PSA response rates will be compared by treatment arm in a stratified logistic regression model, with stratification by race (AA, Other) and bone pain (yes, no).

11.6.2 All binary endpoints in secondary objectives 1-2 and 4-7, will be summarized with point estimates (occurrence rates), and 2-sided Wilson type 95% CIs. The analysis of toxicity rates will be performed using only the toxicity-evaluable (t-e) patients (defined in Section 8.11).

11.6.3 For secondary objective 4, the grade of each type of toxicity (an ordinal categorical variable) will be summarized with 1-way frequency distributions. A similar descriptive analysis will be performed for any correlatives in secondary objective 7 to be assayed by IHC, resulting in ordinal categorical variables (intensity levels of 0, 1+, 2+, or 3+).

Dichotomized versions (e.g., the occurrence rate of Grade 3-4 neutropenia) will be summarized as described in Section 11.6.2. A similar descriptive analysis will be performed for the presence/absence of any correlatives in secondary objective 7 to be assayed by IHC, with presence defined as intensity level of 1+ through 3+.

For any correlatives in secondary objective 7 that are assayed in both pre- and post-treatment prostate tumor tissues, the change in IHC expression level will be described using a 2-way frequency distribution. If the effective sample size appears to be sufficient relative to the size of the 2-way table, the association of these paired variables can be tested with the exact version of McNemar's test.

11.6.4 All censored time-to-event distributions for secondary objectives 3 and 5 will be estimated with standard Kaplan-Meier (K-M) methodology. Point and CI estimates of the median and various time point-specific rates will be derived from the K-M life table. The censored K-M distributions will be compared with the log-rank test, stratified by race (AA, Other) and bone pain (yes, no).

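### Toxicity is counted without reference to its grade before the randomised drug, so symptoms carried in from earlier ADT inflate both arms' rates and pull the rate ratio toward 1

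*Combined protocol and SAP*

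**What the plan says.** - **Scoring.** The second half of section 8.5 says that all subjective toxicities met during the study are evaluated by the NCI criteria. For the other kind it says "Objective toxicities will be based upon the greatest severity that occurred at any time during a treatment cycle", as opposed to the grade when the next cycle begins. A cycle is not defined for this continuous daily treatment.
- **Analysis.** Section 11.3.5 takes the occurrence rate of each toxicity observed. Section 11.6.2 gives rates with Wilson intervals in the toxicity-evaluable patients, who under 8.11 are all registered patients starting therapy. Section 11.6.3 adds that "the grade of each type of toxicity (an ordinal categorical variable) will be summarized with 1-way frequency distributions". None of these mentions a baseline grade, a treatment-emergent definition or attribution.
- **Prior treatment.** Criterion 1 of section 4.1: "Late induction permitted within 3 months of starting LHRH analogue therapy or antiandrogen". Sections 5.3 and 7.0: "For patients eligible for late induction registration the treatment start date will be the date of initiation of GNRH analogue or antagonist". Section 5.3 adds that these men's visits are adjusted for the length of prior hormone therapy.
- **Timing of grading.** Section 6.0: "Toxicity evaluation will be done monthly for the first 8 visits starting with day 1". In the section 7.0 calendar, however, the Tox row is blank at pre-study and Day 1, and its first entry is at month 1.

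**The concern.** Both arms share the same ADT background, so objective 4 should show what each antiandrogen adds to it. A man who has had two months of LHRH analogue and enters with grade 2 hot flashes that do not change can be tabulated as a grade 2 toxicity of his arm. The backdated start date adds to the problem, because ADT effects from before randomisation can fall inside the nominal treatment period.

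The toxicities affected matter here. Section 2.0 reports more hot flashes and fatigue on enzalutamide than on placebo, and section 3.2 describes the adverse event profile of bicalutamide plus an LHRH analogue as driven mainly by the latter. Criterion 4 of section 4.1 allows earlier megestrol for hot flashes, so the protocol expects some men to arrive with them.

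If baseline symptom grades are not recorded at the time, they cannot be reliably reconstructed at analysis.

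**Working it through.** **The plan's own figure.** The plan gives no sizing or expected rate for toxicity. Its one sample-size figure, 41 evaluable patients per arm (section 11.5.1), reproduces. For 50% vs 75%, one-sided 0.10 and power 0.80, the uncorrected n is 32.9. With the continuity correction, (32.9/4) × (1 + √(1 + 4/(32.9 × 0.25)))² = 40.5, which rounds up to 41. This point does not affect it.

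**Inputs for the illustration**
- Prevalence of hot flashes at entry in late-induction men: 53%. Section 3.2 reports this for bicalutamide combined with an LHRH analogue. Using it as prevalence after at most 3 months of prior ADT is an assumption.
- Late-induction share L: not in the documents. Taken as 25%, 50% and 75%.
- New onset p among men free of the symptom: assumed 30% in arm B and 50% in arm A.
- Carried-in symptoms are assumed to persist unchanged, equally in both arms.

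**Formulas.** Carried-in share b = 0.53L, which gives 0.1325, 0.265 and 0.3975.
- As written: rate = b + (1 − b)p.
- Only new or worse events, over all treated men: rate = (1 − b)p.

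| L | As written, B vs A | Ratio | New or worse, B vs A | Ratio | Difference, either rule |
|---|---|---|---|---|---|
| 25% | 39.3% vs 56.6% | 1.44 | 26.0% vs 43.4% | 1.67 | 17.4 points |
| 50% | 48.6% vs 63.3% | 1.30 | 22.1% vs 36.8% | 1.67 | 14.7 points |
| 75% | 57.8% vs 69.9% | 1.21 | 18.1% vs 30.1% | 1.67 | 12.1 points |

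At L = 0 the two rules agree. At L = 100% the rule as written gives 67.1% vs 76.5%, ratio 1.14.

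**Why the difference does not move.** Under both rules it equals (1 − b)(p_A − p_B), since b cancels in the first. The full 20 points, 50% − 30%, appears only among men without the symptom at baseline.

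**Precision.** The binomial variance term in one arm falls by b(1 − b)(1 − 2p) when only new or worse events are counted. For L = 25%, 50% and 75%, the two-arm sums go from 0.484 to 0.438, 0.482 to 0.404 and 0.454 to 0.359. The standard error of the difference is therefore smaller by 1 − √(0.438/0.484) = 5%, then 8% and 11%. The gain comes from arm B; it is zero at p = 50% and would reverse above that.

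**Second set of assumed rates.** Take new onset of 22% vs 42% (22% is the fatigue rate in section 3.2; 42% is assumed) with b = 0.20. As written: 37.6% vs 53.6%, ratio 1.43. New or worse: 17.6% vs 33.6%, ratio 1.91. The difference is 16 points either way.

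**The case against.** Several parts of the opposing case stand.

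- **The effect on the arm difference.** A reader might infer that the present rule cuts a true 20-point difference to 17, 15 or 12, and that counting only new or worse events would restore it. The algebra above shows otherwise: the risk difference in all treated men is the same under both rules. Only a change of denominator recovers the 20 points.
- **The scope of the severity sentence.** A reader might take it as a worst-grade-ever rule for every toxicity. It covers objective toxicities within a cycle. Hot flashes and fatigue fall under the preceding sentence on subjective toxicities. That sentence sets no worst-grade rule, but it sets no baseline reference either.
- **Laboratory abnormalities.** A reader might infer that every stable abnormality allowed at entry counts as toxicity; the transaminase exclusion, for example, applies only at "Total bilirubin, alanine aminotransferase (ALT) or aspartate aminotransferase (AST) > 2.5 times the upper limit of normal". Section 12.2 treats a test abnormality as an adverse event only if it is clinically consequential, and baseline labs are collected, so change from baseline can be derived. Section 11.6.3 does use neutropenia grade as an example and does not link its tables to 12.2, but this remains the weaker case.
- **Attribution.** The documents do not say that baseline findings count as the randomised drug's toxicity; they are silent. Section 6.0 uses attribution only for dose changes.
- **Consequence.** Carry-over is balanced in expectation, and section 11.6 names no between-arm toxicity test. The effect falls on descriptive rates and intervals.

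These points do not supply a baseline rule. Section 12.2 ties adverse events to study drug use, which helps to exclude symptoms that resolved beforehand but says nothing about those that persist. Section 6.0 may intend grading on day 1, but a site following the calendar would not do it.

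**Conclusion.** The point holds as a gap in how toxicity is defined and collected. Without a pre-dose reference grade, carried-in symptoms inflate absolute toxicity rates in both arms and pull the rate ratio toward 1. In the main illustration, arm B is reported at 39% to 58% where new or worsened events occur in 26% to 18%, and the ratio drops from 1.67 to between 1.44 and 1.21. The size rests on an unstated late-induction share, a proxy prevalence, assumed onset rates and unchanged persistence. The direction needs only that some symptoms persist at similar frequency in both arms.

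The documents do not support reading this as a false difference between arms, or as a loss of risk difference that the counting rule alone would repair. The primary endpoint is untouched. The correction is worth making because it is cheap and because missing baseline symptom grades cannot be reliably recovered later.

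**What to change.** 1. Reconcile section 6.0 with the section 7.0 calendar so that CTCAE grades are recorded on Day 1 before the first dose of randomised drug. Say explicitly that, for late-induction men, this means that dose and not the backdated ADT start.
2. In sections 8.5 and 11.6.2–11.6.3, count toxicities from that dose onward that are new or of higher grade than at the baseline grading.
3. For symptoms common on ADT, such as hot flashes and fatigue, also report rates among men without the symptom at baseline. This is the table that shows the undiluted difference.
4. Keep the unadjusted worst-grade table as a supplement.

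The cost is some wording and one baseline grading at a visit that already includes history and examination. Headline toxicity rates will be lower, which is why the unadjusted table should stay. The sample size does not change.
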